5.2.3 Part II.- Treatment Period (Visit 2~5) and Follow-up (Visit 6)

Laboratory data and results of other tests and evaluation shall be obtained at screening to determine the appropriateness of subject enrolled in this study. Subjects who meet the eligibility criteria will be enrolled and take study drugs. Baseline data (Visit 2), including physical examination, vital sign, ECG, hematology, blood chemistry, HAM-D-17, CGI, HAM-A, MADRS, DSSS, C-SSRS and concomitant medication evaluation, will be collected before dosing study drug. At visits 2, 3 and 4 (weeks 0, 2 and 4), each subject will be dispensed a supply of study drug sufficient for 2-week treatment period. The subjects will be instructed to take one dose (i.e., two capsules) after a meal thrice daily for every week. Subjects will be assessed every two weeks and receive the study drug for next two weeks till the end of trial. At visits 2, 3, 4 and 5, the safety and efficacy parameters will be evaluated by the following items.

- Physical examination: skin, head, neck, eyes, ears, nose, throat, heart, lungs, abdomen (liver, spleen), neurological examination, lymph node and extremities.
- Vital sign: heart rate, blood pressure, body temperature
- ECG
- Hematology: RBC, WBC, platelets, hematocrit, hemoglobin, prothrombin time (PT), partial thromboplastin time (aPTT). If the interval of visit 1 and visit 2 is within 7 days, Hematology test of visit 2 can be skipped.
- Blood chemistry: AST, ALT, LDH, total bilirubin, BUN, serum creatinine, free thyroxine (FT4), TSH, sodium, calcium, potassium, LDL, HDL, triglyceride, cholesterol. If the interval of visit 1 and visit 2 is within 7 days, Blood chemistry test of visit 2 can be skipped.
- HAM-D-17, CGI, HAM-A, DSSS, MADRS, C-SSRS and concomitant medication evaluation.
- AE/SAE evaluation
- Drug accountability

Follow-up visit will be performed at visit 6 after one week of the last dose administration.

The test items are outlined in the following:

- Physical examination: skin, head, neck, eyes, ears, nose, throat, heart, lungs, abdomen (liver, spleen), neurological examination, lymph node and extremities.
- Vital sign: heart rate, blood pressure, body temperature
- ECG
- Hematology: RBC, WBC, platelets, hematocrit, hemoglobin, prothrombin time (PT), partial thromboplastin time (aPTT)
- Blood chemistry: AST, ALT, LDH, total bilirubin, BUN, serum creatinine, free thyroxine (FT4), TSH, sodium, calcium, potassium, LDL, HDL, triglyceride, cholesterol.
- HAM-D-17, MADRS, DSSS, CGI, HAM-A and C-SSRS and concomitant medication evaluation.
- Pregnancy test
- AE/SAE evaluation

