1.2.2 Safety Pharmacology

In order to verify the possible effects other than antidepressant, five studies were conducted to evaluate the effects of PDC-1421 on central nervous system, autonomic system, cardiovascular function, respiratory function, gastrointestinal system, renal function, allergy, inflammation, metabolism and hERG tail current assay:

- EfficacyProfiling *in vivo*[®]

- Safety Pharmacology Testing Package
- AdverseEventProfiling *in vivo*®
- Safety Pharmacology test in Central Nervous System, Cardiovascular System and Respiratory System
- hERG tail current assay

The significant findings were summarized in Table 6.

Table 6. Summary of the finding in safety pharmacology

Study package	Study condition and findings
EfficacyProfiling	
 • Oral administration of PDC-1421 at 3000 mg/kg did not cause any significant change in vivo studies. • PDC-1421 at 300 µg/ml did not demonstrate any significant activity ($\geq 50\%$ change) in vitro studies.
Safety Pharmacology Testing Package	
PDC-1421 concentration at 300 µg/mL:
 
 • Decrease in acetylcholine and BaCl₂-induced constriction in guinea pig ileum.
AdverseEventProfiling in vivo ®	
PDC-1421 oral dose at 3000 mg/kg:
 
 • Inhibition of gastric emptying in fasted rats (-45%) 
PDC-1421 oral dose at 3000 mg/kg for 7 days:
 
 • Increase in RBC on day 2 in blood chemistry • Increase in K⁺ and decrease in glucose on day 2 in blood chemistry • Decrease in LDH (lactate dehydrogenase) on day 8 in blood chemistry
Safety Pharmacology test in Cardiovascular System	
 • RR interval elongation, heart rate decrease, diastolic arterial pressure decrease and increased sinoatrial arrest incidence were found in dogs in 2500mg/kg group. • Diastolic arterial pressure decrease was found in dogs in 2500mg/kg group.
hERG tail current assay	Below the dosage, 0.8mg/ml PDC-1421, should be viewed as the “no effect concentration” in this assay.

Few effects, including gastrointestinal effects, electrolytes equilibrium, blood sugar value, heart rate decrease and diastolic arterial pressure decrease were found in safety pharmacology. These findings provided scientific evidence in further clinical study to evaluate the influence of PDC-1421.

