1.5 Dosage Regimen

Based on the FDA's guidance documents, NOAELs from toxicity studies were used to estimate the starting dose in our study. Table 10 summarizes the MRSD for 60 kg human/day calculated from the NOAEL of 28 day repeating dose studies in rats and in dogs using safety margin at 75-fold.

Table 10. Calculation of starting dose

Study	Species	Dosage	HED	Dose for 60 kg human/day
28-day repeated dose subacute oral toxicity study in rats	rat	3000 mg/kg (NOAEL)	483.9 mg/kg	387 mg/day (MRSD)
28-day repeated dose subacute oral toxicity study in dogs	dog	3000 mg/kg (NOAEL)	1666.7 mg/kg	1333 mg/day (MRSD)

Based on these calculations, we proposed the starting dose of PDC-1421 to be at 380 mg/day. In the phase I study, a single dose of PDC-1421 (oral administration) was used to evaluate the safety when taken by healthy subjects. The starting dose and dosage regimen are:

380 mg PDC-1421 (one capsule of PDC-1421 Capsule) once daily after meal.

The dose escalation as follows.

Cohort A (one capsule; 380 mg):

Cohort A enrolled 9 subjects. Seven subjects received PDC-1421 Capsule and two received placebo. There was only one of placebo subjects who met a DLT due to the glucose value at 24 hours after drug administration. We continued the study to the next higher dosage, cohort B.

Cohort B (three capsules; 1140 mg):

Cohort B enrolled 8 subjects. Six subjects received PDC-1421 Capsule and two received placebo. There was only one of placebo subjects who met a DLT due to the glucose value at 4 hours after drug administration. We continued the study to the next higher dosage, cohort C.

Cohort C (six capsules; 2280 mg):

Cohort C enrolled 4 subjects. Three subjects received PDC-1421 Capsule and one received placebo. There was no DLT in this cohort. We continued the study to the next higher dosage, cohort D.

Cohort D (ten capsules; 3800 mg):

Cohort D enrolled 9 subjects. Seven received PDC-1421 Capsule and two received placebo. There is no DLT in the final cohort.

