5.2.1 Screening Phase (Visit 1)

The Screening phase will be done within 1-2 weeks period and intended for diagnosing and assessing the patient for possible inclusion in the study and for providing an adequate washout period. The items of physical, rating scales, laboratory examination and drug accountability at screening are outlined below:

- Informed consent
- Subject information, including date of birth, body height and weight
- Medical history, including any clinically significant psychiatric, neurological, gastrointestinal, renal, hepatic, cardiovascular, respiratory, metabolic, endocrine, hematological or other major disorders
- Drug screen, including alcohol, benzodiazepine, amphetamine/MDMA, opiates, cannabinoid, cocaine, phencyclidine, and barbiturate. If a positive result is determined to be caused by prescription of benzodiazepine instead of subject's drug abuse, a 10-day washout period of the prescribed benzodiazepine is required before being treated with investigational products.
- Pregnancy test
- Physical examination: skin, head, neck, eyes, ears, nose, throat, heart, lungs, abdomen (liver, spleen), neurological examination, lymph node and extremities.
- Vital sign: heart rate, blood pressure, body temperature
- ECG
- Hematology: RBC, WBC, platelets, hematocrit, hemoglobin, prothrombin time (PT), partial thromboplastin time (aPTT)
- Blood chemistry: AST, ALT, LDH, total bilirubin, BUN, serum creatinine, free thyroxine (FT4), TSH, sodium, calcium, potassium, HbA1c, LDL, HDL, triglyceride, cholesterol.
- DSM-IV-TR, HAM-D-17, CGI, MADRS, DSSS, HAM-A, C-SSRS and concomitant medication evaluation.

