5.2.2. Part I. - Treatment Period (Visit 2~7) and Follow-up (Visit 8)

Laboratory data, other tests and evaluation results shall be obtained at Screening to determine the appropriateness of subject enrolled in this study. Subjects who meet the eligibility criteria will be enrolled and take test drug at this period. First six eligible subjects will take 1 capsule of PDC-1421 Capsule thrice daily in the first week and be assessed twice in the first week after drug administration. They will receive 21 packs of PDC-1421 Capsule for the following week and be evaluated every week till visit 8. After one week of the last dose administration, subjects are assessed for a follow-up. Then, a checkpoint will be conducted. If subjects have no serious adverse event, the trial can continue to next step. If subjects have serious adverse events, there should be a meeting to consider the possibility of continuing the next step of the study or not. Another six subjects will take 2 capsules of PDC-1421 Capsule and all the visits are the same as previous three subjects'. Then, another checkpoint will be conducted as mentioned above. If subjects have no serious adverse events, the schedule can be conducted to the part II. If subjects have serious adverse events, there should be a meeting to consider the possibility of continuing part II of the study or not. The items of safety and efficacy parameters at treatment period are outlined below:

- Physical examination: skin, head, neck, eyes, ears, nose, throat, heart, lungs, abdomen (liver, spleen), neurological examination, lymph node and extremities.
- Vital sign: heart rate, blood pressure, body temperature
- ECG
- Hematology: RBC, WBC, platelets, hematocrit, hemoglobin, prothrombin time (PT), partial thromboplastin time (aPTT)
- Blood chemistry: AST, ALT, LDH, total bilirubin, BUN, serum creatinine, free thyroxine (FT4), TSH, sodium, calcium, potassium, LDL, HDL, triglyceride, cholesterol
- HAM-D-17, CGI, HAM-A, DSSS, MADRS, C-SSRS and concomitant medication evaluation. (At visit 3, subjects will not need to be assessed for above scales except C-SSRS and concomitant medication evaluation.)
- AE/SAE evaluation
- Drug accountability

Follow-up visit will be performed at visit 8 after one week of the last dose administration.

The test items are outlined in the following:

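### No Phase II chemistry panel lists glucose, so a blood sugar effect named in the protocol cannot be measured as a change from baseline or compared with placebo

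*Protocol*

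**What the plan says.** Table 6 in protocol section 1.2.2 reports, for oral dosing at 3000 mg/kg over 7 days, "Increase in K⁺ and decrease in glucose on day 2 in blood chemistry". The summary below the table states: "Few effects, including gastrointestinal effects, electrolytes equilibrium, blood sugar value, heart rate decrease and diastolic arterial pressure decrease were found in safety pharmacology". It then says, in general terms, that these findings inform later clinical study of the product.

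Section 1.4.1 (Potential Risk) carries forward electrolyte changes and gastrointestinal discomfort, and adds cardiovascular monitoring. It does not mention blood sugar.

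The screening chemistry list (5.2.1) ends "TSH, sodium, calcium, potassium, HbA1c, LDL, HDL, triglyceride, cholesterol". The Part I lists (5.2.2) end "sodium, calcium, potassium, LDL, HDL, triglyceride, cholesterol", without HbA1c. The Part II list (5.2.3), given once for treatment and once for follow-up, is "Blood chemistry: AST, ALT, LDH, total bilirubin, BUN, serum creatinine, free thyroxine (FT4), TSH, sodium, calcium, potassium, LDL, HDL, triglyceride, cholesterol".

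Phase I was a single-dose study in healthy subjects, and glucose was measured there. For cohort A, section 1.5 says: "There was only one of placebo subjects who met a DLT due to the glucose value at 24 hours after drug administration". It reports a second such event, at 4 hours, in a placebo subject of cohort B. Section 1.3 describes two grade 2 glucose values at the same times in the same cohorts, both on placebo, with no intervention needed.

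SAP 6.5.3 plans descriptive statistics of values and net changes for hematology and biochemistry, which covers only the analytes collected.

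**The concern.** The protocol identifies an effect in its own nonclinical data and then does not schedule the test that would show whether it occurs in patients. The other effects named in the same sentence all have some form of capture after dosing. The timing also matters. The animal change was seen under repeated dosing, Phase I gave single doses, and this trial gives the product three times daily for 28 days (Part I) or 42 days (Part II). With no glucose assay and no later HbA1c, the study report could not describe glycaemic change on treatment, and it could not use the placebo arm of Part II to put such change in context.

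**Working it through.** **1. Effects named in 1.2.2 against Phase II capture after dosing**

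| Effect named | Capture in Phase II |
|---|---|
| Gastrointestinal | Adverse event reporting (7.3) |
| Electrolytes | Sodium, calcium and potassium in chemistry |
| Heart rate | Vital signs, ECG |
| Diastolic pressure | Vital signs |
| Blood sugar | No scheduled measurement |

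RBC and LDH, which Table 6 also flags, are in the Phase II panels.

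**2. The five chemistry lists**

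| List | Analytes | Glucose | HbA1c |
|---|---|---|---|
| Screening, Visit 1 (5.2.1) | 16 | no | yes |
| Part I treatment (5.2.2) | 15 | no | no |
| Part I follow-up (5.2.2) | 15 | no | no |
| Part II treatment (5.2.3) | 15 | no | no |
| Part II follow-up (5.2.3) | 15 | no | no |

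Glucose is in 0 of 5 lists and HbA1c in 1 of 5. One pre-dose HbA1c gives no change from baseline.

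**3. Laboratory visits affected** (Tables 15 and 16)

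- Part I chemistry after screening: Visits 2, 5, 7 and 8, of which 3 follow the first dose.
- Part II chemistry after screening: Visits 2 to 6, of which 4 follow the first dose. Visit 2 may be skipped if it falls within 7 days of Visit 1.
- Planned post-dose chemistry samples with full attendance: 12 × 3 + 60 × 4 = 36 + 240 = 276. None is assayed for glucose.

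**4. The Phase I events**

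- The enrolled total reproduces: PDC-1421 7 + 6 + 3 + 7 = 23, placebo 2 + 2 + 1 + 2 = 7, and 23 + 7 = 30, as section 1.3 states.
- Dose-limiting glucose values on PDC-1421: 0/23. Exact two-sided 95% upper limit: 1 − 0.025^(1/23) = 14.8%.
- Dose-limiting glucose values on placebo: 2/7 = 28.6%, exact 95% CI 3.7% to 71.0%.
- Probability that both events fall on placebo by chance: (7/30) × (6/29) = 42/870 = 0.048, which is also the Fisher exact two-sided p-value. Any imbalance is against placebo.

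**5. Exposure behind the animal signal**

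The species for the 7-day finding is not stated, so two assumptions are shown. Both compare with the top Phase II daily dose of 2280 mg.

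- If rat: the human equivalent of 3000 mg/kg in Table 10 is 483.9 mg/kg, and 483.9 × 60 kg = 29,034 mg. Ratio 29,034/2280 = 12.7.
- If mouse: section 1.5 equates 100 mg/kg with about 480 mg, so 3000 mg/kg is about 30 × 480 = 14,400 mg. Ratio 14,400/2280 = 6.3.

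**6. What the added assay could show**

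With about 20 subjects per arm, the 95% interval for a difference between two arm means has a half-width of about 1.96 × √(1/20 + 1/20) = 0.62 standard deviations. That supports description only.

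**The case against.** The case for leaving glucose out has substance. The animal signal is one change on day 2 at a dose roughly 6 to 13 times the top Phase II daily dose under the assumptions above. For day 8 of the same work, Table 6 lists only LDH. The 28-day rat and dog summaries do not name glucose, and the 13-week rat study reports no toxicity in serum chemistry, although none of these sections itemises glucose. Phase I did measure it, and section 1.3 reports only mild laboratory changes on PDC-1421 with no relation to dose. The closing sentence of 1.2.2 is too vague to count as a commitment to measure each analyte in Phase II. All of this stands, and it limits the weight of the point. It does not remove it: Phase I was single-dose, and section 1.4.1 gives no reason for leaving blood sugar out.

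Two stronger readings are tempting, and the documents support neither.

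- A reader might infer from the Phase I dose-limiting glucose values that the product disturbs glucose. Both were in placebo subjects, none of the 23 on PDC-1421 had one, and the text does not say whether the values were high or low. They show only that glucose values are hard to interpret without a concurrent placebo arm. Part II has one; Part I does not.
- A reader might infer that a glucose effect could not be noticed at all. Section 7.3 counts clinically significant findings as adverse events, including those the investigator judges relevant. Section 5.2.2 also refers to a separate data and safety monitoring plan that is not among the documents. What is missing is a scheduled measurement.

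**Conclusion.** The point holds in a limited form. The protocol names blood sugar as a safety-pharmacology effect, drops it from the risks carried forward without giving a reason, and schedules no glucose at any of the seven post-dose laboratory visits. No laboratory glucose change from baseline can be calculated or compared between arms. Only disturbances that surface as adverse events would be recorded.

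This is a modest gap in safety data. It has no bearing on the primary endpoint, the hypothesis tests or the efficacy conclusions. The conclusion assumes that the chemistry lists in 5.2.1 to 5.2.3 are complete, and that the single-dose Phase I study is the only earlier human exposure, since the documents describe no other.

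**What to change.** Add serum glucose to the blood chemistry lists in protocol 5.2.1, 5.2.2 and 5.2.3, run on the samples already drawn at the scheduled laboratory visits, and record the time since the last meal. Include glucose in the descriptive tables under SAP 6.5.3. Where Part II Visit 2 chemistry is skipped, state that the Visit 1 value serves as baseline; section 7.2 sets baseline at Visit 2 and offers no substitute.

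The cost is one routine assay and one or two CRF fields, with no extra visit or blood draw. Values not taken fasting will be noisier, and at about 20 per arm the comparison will be rough and descriptive. Part I values will have no concurrent control.

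If the sponsor prefers not to add the assay, section 1.4.1 should say why the finding in 1.2.2 needs no follow-up. If sampling is already complete, the study report should state that glucose was not measured on treatment.

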5.3 Other Medication During the Study

To avoid conflict or unknown effects with the study drug, subjects are prohibited from taking any antidepressants and psychoactive drugs, as per the exclusion criteria, including MAOIs (monoamine oxidase inhibitor), NRIs (norepinephrine reuptake inhibitor) and norepinephrine receptor agonist/antagonist. Subjects can't combine the newly-initiated psychotherapy. If subjects have severe insomnia, Zolpidem, Zopiclone or Zaleplon can be used in four nights per week from V1 to the first week after V2. (The maximum daily dose in Zolpidem, Zopiclone and Zaleplon are 10 mg, 7.5 mg and 10 mg respectively.)

6 EFFICACY ASSESSMENTS

6.1 Specification of the efficacy parameters

Efficacy parameters are outlined as follows:

- MADRS evaluation
- CGI evaluation
- HAM-D-17 evaluation
- HAM-A evaluation
- DSSS evaluation

6.2 Methods and Timing for Assessing, Recording, and Analyzing of Efficacy Parameters.

The data obtained from eligible subjects before study drug administration in Visit 2 are set as baseline. After the beginning of treatment, the collection of data of efficacy parameters are performed at planned treatment schedule as section 5.2. CRC shall record these data in CRF in detail after each visit during the treatment period. In part I, efficacy assessments are conducted from screening stage to the last visit. In part II, data

comparison between group of 1 capsule TID, 2 capsules TID of PDC-1421 Capsule and placebo will be conducted in final report of this study to evaluate which group(s) of PDC-1421 Capsule are efficient. The rating scales are as follows:

- **MADRS (Montgomery- Å sbergDepression Rating Scale)**

The MADRS is a 10-item checklist including 1) depression [apparent]; 2) depression [reported]; 3) loss of interest; 4) suicidal ideation; 5) tension; 6) reduced appetite; 7) insomnia; 8) difficulty in activities; 9) concentration; and 10) pessimism. Each Item is rated on a scale of 0-6, with anchors at 2-point intervals; higher scores indicating more severity (i.e., ranging from 0 [no sadness] to 6 [extremely despondent]). Percentage of partial responders (defined as a participant with a 25-50%decrease from baseline in total score) and responders (defined as a participant with $\geq 50\%$ decrease from baseline in total score.). The following are as an interpretation of scores:

Recovered, 7

Mild, 15

Moderate, 25

Severe, 31

Very severe, 44

- **CGI (Clinical Global Impression)**

The CGI actually comprises two companion one-item measures evaluating the following: (a) CGI-Severity (CGI-S) which rates illness severity of psychopathology from 1 to 7 and (b) CGI-Improvement (CGI-I) which rates change from the initiation (baseline) of treatment.

- **HAM-D-17 (Hamilton Rating Scale for Depression)**

This is one of the earliest scales to be developed for depression, and is a clinician rated scale aimed at assessing depression severity among patients for treatment. There are four specific HAM-D symptom groups: psychomotor retardation, anxiety, cognitive disturbance and insomnia. The depression score ranges from 0 to 52. The following are as an interpretation of scores:

0-7: Normal

8-16: Mild

17-23: Moderate

≥24: Severe

- **HAM-A (Hamilton Rating Scale for anxiety)**

HAM-A is a series of questions related to symptoms of anxiety. It rates the individual on a five-point scale (0~4) for each of the 14 items. Seven of the items specifically address psychic anxiety and the remaining seven items address somatic anxiety. The anxiety score ranges from 0 to 56, lower scores are better. The following are as an interpretation of scores:

0-13: Normal

14-17: Mild

18-24: Moderate

≥25: Severe

- **DSSS (Depression and Somatic Symptoms Scale)**

The scale includes a simultaneous measure of depression and somatic symptoms that two issues frequently co-occur. Though many preexisting questionnaires for depression contain items relating to somatic complaints, the DSSS is specifically concerned with the relationship between the two. Consisting of 22 items, the DSSS includes 12 depression-related items and 10 somatic items. Evaluation of the severity of the symptoms are the following:

Absent: no symptoms

Mild: symptoms caused slight discomfort or disturbance

Moderate: symptoms caused significant discomfort or disturbance

Severe: symptoms caused very significant discomfort or disturbance

7 SAFETY ASSESSMENTS

7.1 Specification of Safety Parameters

Safety parameters are outlined as follows:

- Data collected from the physical examinations, vital sign, ECG and laboratory test in scheduled visit
- Adverse events reported
- Serious adverse events reported
- C-SSRS evaluation

7.2 Methods and Timing for Assessing, Recording, and Analyzing of Safety Parameters

The data obtained before study drug administration in Visit 2 are set as baseline. After the beginning of treatment, the collection of data of safety parameters are performed at planned treatment schedule as section 5.2. AE or SAE will be closely monitored during the study period. CRC shall record these data in CRF in detail. In part I and part II, data are recorded from screening stage to the last visit.

